## **A1. BACKGROUND AND SIGNIFICANCE**

**Depression and Veterans' health, functioning, and quality of life.** Depression prevalence among OEF/OIF Veterans is high (e.g., 59% screened positive; Seal et al, 2008), with increasing rates among this cohort of Veterans over the past few decades (Seal, 2009), making depression the most prevalent mental health concern in the VA. Although some recover quickly, the majority experience recurrent and often chronic depression (Whiteford, 2013). By the third episode, a person with a history of depression is 90% likely to experience another episode, highlighting the critical role of early intervention and care. Depression is a vastly heterogeneous syndrome (Monroe & Harkness, 2012) primarily characterized by low mood and anhedonia. Among Veterans, depression is a comorbid condition that complicates the course of PTSD and TBI recovery. Depressed people are 30 times more likely to commit suicide than are healthy individuals (Joiner, 2010) and 5 times more likely to abuse substances. The prevalence of depression and its associated morbidity and mortality make care for depression a high priority in the VA (DVA/DoD, 2016).

**Depression care in the VA.** Cognitive behavioral psychotherapies and psychotropic medications are recommended by VA practice guidelines and are available as first line treatments for depression, yet Veterans often do not **engage** (i.e., initiate, adhere) in offered care. Despite great efforts to promote evidence-based treatments (EBTs) as the gold standard of care for depression and to increase access to mental health care in the VA (Mott, 2014), **any mental health care utilization among veterans continues to be low** (i.e., 18.5-27%; Burnam, 2009; Mott, 2014). Low utilization of care highlights a major gap in the guidelines for depression care in the VHA. VA clinical practice guidelines for the management of major depressive disorder (MDD; VHA/DoD, V3, 2016) omits any discussion of the management of patients who require clinical care but disengage. Given the sequelae of untreated depression, it is paramount to both identify those at risk for dropping out of care and develop strategies for management of patients that prematurely disengage from traditional care.

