**Data processing.** Data will be initially checked for out of range values and missing data where appropriate through plotting and descriptive analyses. Data will be transformed as needed. Logistic regression is relatively free of restrictions and can accommodate a mix of predictors (continuous, discrete, dichotomous) (Tabachnick & Fidell, 2007). *With continuous predictors, the assumption is that there is a monotonic relationship (increase or decrease) between the predictor variable and odds of the binary outcome (i.e. engagement or lack of engagement in care). The functional of this linear assumption can be evaluated by use categorical indicator variables as well as transformations of the continuous variable, such as a quadratic form. Multicollinearity will be tested using two approaches. First, we will explore correlations among IVs and exclude variables based on high correlations ( $> .65$ ). Second, we will examine the size of the standard error (SEs) relative to the beta coefficient for each predictor in the model. Large SEs will be indicative of potential multicollinearity. Residuals will be tested to identify possible outliers.*

Analysis plan:

**Modeling risk for lack of treatment engagement.** For all analyses, lack of treatment engagement is the main dependent variable and will be investigated using three related definitions based on the date in which a PHQ9 score  $\geq 10$  is identified in the EHR. Specifically, we will examine whether treatment is initiated within 3-months, 6-months, or 12-months from the date of the PHQ9 assessment. *Independent variables of interest will be extracted based on proposed framework, empirical evidence, and availability in the EHR (see Table 1), including insight from a select number of semi structured surveys collected prior to data analysis (described below).*

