*Fortunately, the EHR is rich in terms of wealth of potential predictors to carry out the analyses. This work is a first step in the development of an automated system that can be implemented in the VHA EHR to more easily identify patients who may be in need but at risk for lack of engagement in mental health treatment.* A direct logistic regression will be performed to evaluate the battery of proposed and potential factors as possible predictors of lack of treatment engagement. The final model will be estimated using the validation sample (half of our overall available sample). Regression (beta) coefficients and odds ratios will be extracted for interpretation and evaluation of risk to not engage in treatment in our next step.

*Computation of health service utilization risk score.* Using coefficients extracted from final logistic regression testing the best fitting patient phenotype associated with lack of treatment engagement, we will compute a risk score for lack of treatment engagement. This score will be used to select high risk patients enrolled in our intervention development and evaluation studies (Aims 2 and 3). The logistic regression equation will be used to calculate the risk scores using the intercept and co-variated specific coefficients that relate to the probability of lack of treatment initiation. Therefore, the equation will be based on the logistic regression model which will be developed in the log odds scale.

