*Machine learning process.* This step of the data analysis will be conducted to assess the extent to which machine learning methods can potentially improve upon the prediction accuracy derived from the conventional logistic regression analysis. As with the conventional logistic regression analysis, the cohort of 88,456 OEF/OIF Veterans will be used. A range of machine learning methods will be used to compare results on variable importance and interpretability, with the goal of providing insight for clinicians on potential risk mitigation strategies for veterans at risk of not engaging in treatment for depression. The methods to be compared will include Lasso penalized logistic regression (Tibshirani 1996), random decision forests (Liaw 2002), decision trees (Hastie 2009), and support vector machines (Hastie, 2001). Each approach offers potential pros and cons in terms of modeling complex data and in interpretation. For example, decision trees accommodate high dimensions, model non-linear relationships, and perform well with missing data and are highly interpretable by humans. Support vector machines provide automated scaling of predictor variables and support linear and polynomial kernels for model training. Regardless of the method used, to prevent overfitting, 10-fold cross validation will be employed. This process splits the data into ten separate sets and builds a model on each set using the other nine sets. Variance across the ten models will be examined to evaluate model stability. Model performance will be evaluated using the standard F-Measure which is the harmonic mean of precision and recall. This will be augmented with use on metrics of predictive performance including area under the curve (AUC), sensitivity, and specificity, with a focus on clinical interpretability. Error analysis will be employed to improve model performance on 10 separate samples until model performance is maximized on the test set and then validated on the final set. As models are being developed, pruning algorithms will be used to make the model more generalizable. Finally, although there are no specific guidelines or power analysis for the determination of the exact sample size needed for specific models, generally samples such as  $n > 1000$  have been found to be adequate for machine learning. Our sample for this step of the analysis will be  $N = 88,456$  and we will be using the sample to its fullest. Therefore, we propose to use 10 ( $n = \sim 7000$ ) samples as training sets to test and fine-tune our phenotype model. We will use 2 additional ( $n = \sim 9000$ ) samples to do a final model testing and finally validate the model.

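### The lead metric for comparing Aim 1 models is the F-measure, with no rule for which metric decides; if non-engagement is common, F barely separates models and depends mainly on the cut-off.

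*Protocol*

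**What the plan says.** All the relevant text is in the protocol; the SAP does not cover Aim 1 modelling.

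- **Lead metric.** Section A4a, under the machine learning process: "Model performance will be evaluated using the standard F-Measure which is the harmonic mean of precision and recall".
- **Supplements.** The next sentence: "This will be augmented with use on metrics of predictive performance including area under the curve (AUC), sensitivity, and specificity". No order of priority is given. A later sentence has models refined until performance on the test set is as high as possible, without naming the measure.
- **Outcome.** Section A4a, analysis plan: "For all analyses, lack of treatment engagement is the main dependent variable". Three windows are used: "we will examine whether treatment is initiated within 3-months, 6-months, or 12-months from the date of the PHQ9 assessment". Table 1, by contrast, lists treatment initiation as the outcome, and the concordant/discordant analysis speaks of predicted scores for engagement. The positive class for F is not stated.
- **Model choice and use.** The A4a overview aims for the best model on prediction performance and interpretation, whether logistic or machine learning. Of the resulting risk score the plan says: "This score will be used to select high risk patients enrolled in our intervention development and evaluation studies".
- **Cut-off.** For Stage 1 the overview derives it from ROC analysis. No cut-off rule is given for Stage 2.
- **Prevalence.** No non-engagement rate is given for the cohort of 88,456. The nearest figure is in section A1, which says that "any mental health care utilization among veterans continues to be low" and puts it at 18.5-27%.

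**The concern.** F is built from precision and recall, so it gives no credit for true negatives, and its value depends on both prevalence and cut-off. When the positive class is the majority, a rule that calls everyone positive already has perfect recall and high precision. A genuine model then has little room to score higher, and it can score lower if its cut-off balances sensitivity against specificity.

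This matters because Stage 2 is meant to show whether machine learning improves on logistic regression. Stage 1 has an ROC-derived cut-off and Stage 2 has none stated. If F decides, one approach could win because of where its threshold sits rather than how well it ranks patients. Ranking is what a score for picking out high-risk patients needs. The three windows may also have three prevalences, so F values cannot be compared across them without a reference value.

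**Working it through.** The plan gives no F value or prevalence to reproduce, so this is a check under stated assumptions.

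**Inputs**
- Non-engagement prevalence p: 1 - 0.27 = 0.73 and 1 - 0.185 = 0.815, from section A1. Applying these to the Aim 1 cohort is an assumption; lower values are shown in step 4.
- Positive class: lack of engagement (assumption; reversed in step 5).
- AUC 0.8, the protocol's own example of good fit in section A4a.
- Equal-variance binormal ROC (assumption): d' = √2 × z(0.8) = 1.190.

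**Formula.** F = 2·p·Se / [p·Se + (1 - p)(1 - Sp) + p].

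**Step 1: flag everyone.** Se = 1 and Sp = 0, so F = 2p/(1 + p).
- p = 0.73: 1.46/1.73 = 0.844
- p = 0.815: 1.63/1.815 = 0.898

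**Step 2: AUC 0.8 model at the cut-off that maximises F.**
- p = 0.73: best F 0.864, gain 0.020. Se 0.95, Sp 0.32; 88% of patients flagged.
- p = 0.815: best F 0.906, gain 0.008. Se 0.98, Sp 0.21; 94% flagged.

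At AUC 0.7 the best F is 0.847 and 0.899, a gain of 0.003 or less. At AUC 0.9 it is 0.901 and 0.929, a gain of 0.057 and 0.031. The compression is therefore severe for moderate models and milder for strong ones.

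**Step 3: the same AUC 0.8 model at its Youden cut.** Se = Sp = Φ(1.190/2) = 0.724.
- p = 0.73: p·Se = 0.529; (1 - p)(1 - Sp) = 0.27 × 0.276 = 0.0745; F = 1.057/(0.529 + 0.0745 + 0.73) = 0.793
- p = 0.815: p·Se = 0.590; 0.185 × 0.276 = 0.0510; F = 1.180/(0.590 + 0.0510 + 0.815) = 0.811

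Both are below flag-everyone. For one and the same model, moving the cut-off changes F by 0.864 - 0.793 = 0.071 and 0.906 - 0.811 = 0.095. That is more than the change in best F between AUC 0.7 and AUC 0.9 (0.901 - 0.847 = 0.054; 0.929 - 0.899 = 0.030).

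**Step 4: lower prevalence, AUC 0.8.**

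| Non-engagement | Flag-everyone F | Best F | Gain |
|---|---|---|---|
| 60% | 0.750 | 0.797 | 0.047 |
| 50% | 0.667 | 0.743 | 0.076 |
| 30% | 0.462 | 0.612 | 0.150 |

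**Step 5: engagement as the positive class, AUC 0.8.** At 27%, flag-everyone scores 0.425 and the best F is 0.587. At 18.5% the figures are 0.312 and 0.507. The gain is 0.16-0.19.

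**The case against.** - **F is not read alone.** The supplementary metrics would show a literal flag-everyone rule at once (AUC 0.5, specificity 0). This stands. A reader might infer that a useless rule could pass as a good model; the documents do not support that. What remains is that no rule says which metric decides when they disagree.
- **The recruitment cut-off.** A reader might infer that nearly everyone would be selected, so that recruitment by risk score would target no one. The documents do not support that either. Stage 1 takes its cut-off from ROC analysis, and nowhere is a cut-off set by maximising F. At AUC 0.8 a Youden cut would flag about 60% (p = 0.73) to 64% (p = 0.815).
- **The prevalence is borrowed.** The background rate is for any mental health care among veterans. The cohort has PHQ9 scores of at least 10 and is not already in treatment, and a primary care visit with a depression code counts as initiation. This stands, and step 4 shows how far it matters.
- **The positive class is not stated.** This also stands. If it is engagement, the problem largely goes away.
- **A small gain is not a tie.** With about 9,000 held-out records (the planned set size), simulation puts the standard error of the gain over flag-everyone at about 0.002 at p = 0.73 and 0.001 at p = 0.815. Gains of 0.020 and 0.008 would be detectable, and best F still rises with AUC. That protects the ranking of models only if each is scored at its own F-optimal cut, which the plan does not specify.
- **Modest stakes.** The score selects 6 patients in Aim 2 and 15 in Aim 3, both formative. This limits the consequence, but the model choice is itself an Aim 1 result.

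**Conclusion.** The concern holds in a conditional form. The plan leads with a metric that depends on prevalence and threshold, names no positive class for it, and does not say which metric decides. If non-engagement is about 73-81.5% and is the positive class, an AUC 0.8 model gains only 0.008-0.020 in F over flagging everyone, and at its Youden cut falls below that reference. The logistic versus machine-learning comparison could therefore be distorted by the threshold alone.

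The size rests on three assumptions: the background utilization rate applies to the cohort, lack of engagement is the positive class, and the ROC is equal-variance binormal. The first two could fail, and the problem then shrinks or largely disappears. The change is worth making because it removes the dependence on both at little cost.

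**What to change.** In section A4a, under the machine learning process:

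1. Make held-out AUC, already planned, the deciding metric for tuning and for choosing between logistic and machine-learning models, computed on the same held-out records for all of them.
2. Report calibration for models that output probabilities.
3. Report sensitivity, specificity and positive predictive value at the ROC-derived recruitment cut-off.
4. Keep F as a secondary figure. Name its positive class, and give the observed prevalence and the flag-everyone F for each of the 3-, 6- and 12-month windows.

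Cost: no new data, since these quantities come from predictions the plan already produces. F results become secondary, and support vector machines need an extra step to give probabilities for calibration.

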
Table 1. List of variables extracted from electronic medical record data.

Observed Independent Variables	
Demographics	Age, gender, race/ethnicity, marital status, service connected disability.
Non-psychiatric illness	Elixhauser measure
Depression diagnoses	ICD-9 Depression Codes e.g., 296.2-296.36; 293.83; 309.0.
Anxiety Disorders/ PTSD diagnoses	ICD-9 CM codes for Anxiety and Stress-related conditions e.g., 293.84; 309.24; 309.28; 309.81; 300.00-300.09.
Serious Mental Illness diagnoses	ICD9-CM codes for Bipolar Affective Disorder Type 1, Schizophrenia e.g., 293.81-293.83; 296.40-296.7; 295.40-295.90; 296.56-293.83.

Alcohol/Substance Use Disorder Diagnoses	ICD9-CM codes for Alcohol, Amphetamine, Cocaine, Inhalant Use Disorders: 291.89-304.40.
Depression severity	PHQ-9 items and scores
Depression chronicity	Time from first to last ICD9 code or time between elevated PHQ9s
Anxiety severity	GAD-7 items and scores
PTSD severity	PCL-5 items and scores
Affective characteristics	PCL-5 clusters C (emotional avoidance), D (negative mood and cognitions), E (arousal and reactivity)
Somatic difficulties	Somatic factor of the PHQ9 (e.g., fatigue, sleeping difficulties)
Instrumental Variables	
Distance to the VA	e.g., GIS tracking, zip code mapping
System approachability	Is the mandatory annual depression screen completed in the past year?; Does pt have PCMH routine check in over the past two years?
Ability to reach VA	Has available transportation/eligible for VA transportation; full time or multiple jobs
Family support	Asian and Black race (as proxy) have been associated with increased social stigma of mental illness, including lack of family/friends support to seek mental health services
Beliefs about care	Gender and race have been associated beliefs about MH care
Unobserved Variables	
Transportation availability	These variables have been repeatedly identified in the literature as barriers to mental health treatment. We will not have this information available in the structured data.
Employment	
Child or family care	
Outcome Measure (Dependent Variable)	

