other barriers that were not gleaned from the literature (see Appendix 3). Such an instrument will help us identify possible instrumental variables and unmeasured unobserved variables. (2) If warranted, IV analysis will also be used to test alternative models. Semi-structured surveys will be completed by 10 patients the PI has access to in the primary care clinic that meet our inclusion criteria (see Table 2) and that were referred to mental health services but missed their appointment based on EHR. (3) Empirical results from the development and validation analyses (described above) will be reviewed. First, if the ROC analysis indicates suboptimal model fit (e.g. AUC <0.8), this alone will suggest that important variables (whether observed or unobserved) were not included in the models. However, assuming overall good model fit (e.g. AUC  $\geq 0.8$ ), the next step will be to assess both “concordant” and “discordant” results. This analysis will again be based on semi structured surveys with 10 veterans who did or did not engage in treatment for depression.

To illustrate, each veteran in the analysis will have both an observed and predicted outcome score (i.e. engagement in treatment). For the “discordant” analysis, a random sample of 5 veterans who had very high predicted scores for engagement in treatment, yet did not engage in treatment, will be asked to complete our semi-structured survey. Emphasis will be on identifying the principal reason(s) for which the veteran did not engage in care despite having a very high predicted engagement score. Similarly, a random sample of 5 veterans who had very low predicted scores for engagement in treatment, yet engaged in treatment, will be asked to identify the reasons that influenced their decision to engage in treatment. For the “concordant” analysis, a random sample of 10 veterans who engaged or did not engage in treatment consistent with their predictive score will complete a semi-structured survey. In this circumstance, emphasis will be on comparing the extent to which rank ordering of the strength of the observed variables (predicted) in the prediction models actually reflected the treatment engagement decision making process employed by the veteran. This qualitative information will provide insight into to validity of the variables used in the prediction models, and again, whether important unobserved variables influenced the veteran’s decision for treatment engagement.

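### The concordant survey compares one cohort-wide ranking of predictors with individual Veterans' decisions; the two would generally differ even under a correct model, so a mismatch is not evidence against a predictor.

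*Protocol*

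**What the plan says.** The step is in the protocol, section A4a (Aim 1), under the steps to control for unobserved variables. The SAP does not cover it.

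- **When it runs.** If the ROC analysis shows good fit, with AUC of at least 0.8 as the example, "the next step will be to assess both “concordant” and “discordant” results".
- **Who is surveyed.** For the concordant part, "a random sample of 10 veterans who engaged or did not engage in treatment consistent with their predictive score" completes a semi-structured survey.
- **What is compared.** On the model side, the "rank ordering of the strength of the observed variables (predicted) in the prediction models actually reflected the treatment engagement decision making process". On the Veteran side, the "decision making process employed by the veteran".
- **What is inferred.** "This qualitative information will provide insight into to validity of the variables used in the prediction models", and also "whether important unobserved variables influenced the veteran’s decision for treatment engagement".
- **Where predictor strength comes from.** For the logistic model, "Regression (beta) coefficients and odds ratios will be extracted for interpretation and evaluation of risk". For the machine learning models, variable importance is compared. Both describe the whole cohort.
- **What the predictors are.** The Aim 1 overview calls them proxy measures taken from the EHR. Table 1 includes age, gender, race/ethnicity, marital status, diagnosis codes, a comorbidity measure and scale scores. It lists transportation, employment and child or family care as unobserved and says of them: "These variables have been repeatedly identified in the literature as barriers to mental health treatment".

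The documents define no per-Veteran contribution, no measure of agreement and no level of agreement to expect from a correct model.

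**The concern.** A ranking by coefficient, odds ratio or variable importance describes what separates people across the cohort. It is the same list for everyone. What pushed one Veteran's score up or down depends on where that Veteran sits on each predictor. The two orderings are different quantities and need not agree when the model is right.

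There is a second reason to expect disagreement. A proxy can predict well without being anything a person would name. A Veteran whose demographic profile predicts non-engagement may answer in terms of child care, and both statements can be true.

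At stake is the validity inference. With no reference level, a reader of ten surveys cannot tell the disagreement expected under a correct model from disagreement that signals a fault. Sound predictors could be described as doubtful in the Aim 1 report, and that model supplies the risk scores used to select patients for Aims 2 and 3.

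**Working it through.** The plan gives no figure for this comparison, so there is none to reproduce. The check has two parts.

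**1. The logic, with two predictors.** Let Veteran i's contribution from predictor j be c_ij = b_j × (x_ij − cohort mean of x_j), with predictors in SD units. Take b_1 = 1 and b_2 = 0.9, so predictor 1 is first in the cohort ranking. A Veteran at the mean on predictor 1 and one SD above on predictor 2 has c_1 = 1 × 0 = 0 and c_2 = 0.9 × 1 = 0.9. This Veteran's own leading driver is predictor 2, although the model is exact.

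**2. How often this happens.** Outcomes were simulated from a known logistic model, and the same true coefficients served as the prediction model. Each simulated Veteran knows his or her own drivers perfectly. Contributions were signed towards the Veteran's own outcome, ranked, and compared with the cohort ranking of coefficients per SD.

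Inputs from the protocol: N = 88,456, and AUC 0.80 as the example threshold. Everything else is assumed:

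- 77% non-engagement. The documents give no rate for this cohort. Section A1 quotes mental health care use of 18.5 to 27% among Veterans, that is 73 to 81.5% non-use, and 77% lies inside that range.
- 8 or 12 independent predictors, with log odds ratios per SD falling by a factor of 0.8 or 0.9 from one to the next.
- Concordant means top risk quartile and not engaged, or bottom quartile and engaged.

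| Setting (model exactly true) | Cohort's top predictor is the Veteran's own top driver | Mean rank correlation |
|---|---|---|
| All predictors continuous | 27–45% | 0.21–0.38 |
| Half the predictors binary, 30% prevalence | 18–71% | 0.15–0.62 |

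A repeat with continuous predictors, or with every second one binary, fell inside these ranges: 27–44% and 28–59%. In that repeat the Veteran's top three were the cohort's top three, in any order, in 4–19%.

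A wider set used 10 predictors, AUC 0.80 or 0.90, a coefficient ratio of 0.9 or 0.7, no intercept (so about half engage), and two definitions of concordant. It gave 16–79% for the top predictor, 0–16% for the top three in order, and a mean rank correlation of 0.15–0.64. The full ranking matched in 0.00%.

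The exception is a dominant predictor. With 4 or 5 predictors and one far stronger than the rest, the top predictor matched in 81–100%. The full ranking still matched in only 0–62%.

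**In terms of the ten surveys.** At 20 to 70% agreement, the expected number matching on the top predictor is 10 × 0.20 = 2 to 10 × 0.70 = 7. Even at 70%, the chance that all ten match is 0.70^10 = 0.028.

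**The case against.** The strongest reply is that nothing here can be failed. The comparison is one of degree, the output is called qualitative, and it is only to give insight. There is no threshold or decision rule. That stands: a reader might infer that the survey passes or fails the model, and the documents do not say so.

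A reader might also infer that Aim 1's conclusion about its model rests on this survey. It does not. The protocol evaluates the profiles and cut-off in a validation sub-cohort and plans cross-validation, AUC, sensitivity, specificity and a final validation set for the machine learning models. The score is computed from the coefficients, and nothing says that survey answers drop a predictor or alter the score.

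Nor do the documents support the reading that the step will declare unobserved variables important whatever the truth. In the simulations every driver is in the model, so they say nothing on that. The section is concerned with observed variables standing in for unobserved causes, and a Veteran who names an unrecorded barrier gives the information it seeks.

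Table 1 is also not one-sided. Under instrumental variables it lists distance, transportation and jobs, although transportation and employment appear again as unobserved. Symptoms such as fatigue and poor sleep are predictors that a person could name. Disagreement is likely but not certain.

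Finally, the simulated agreement exceeds chance, which is 1/12 = 8.3% to 1/8 = 12.5% for the top predictor, so the comparison carries some information. The predictors were taken as independent, whereas Table 1 has nested scales. The interview guide is in an appendix that is not among the documents, so how the comparison would be made in practice cannot be checked.

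None of this rescues the inference from a cohort ranking and individual answers to the validity of a predictor.

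**Conclusion.** The concern holds in a limited form. The concordant analysis sets a cohort-level ranking beside individual decision processes and reads the result as bearing on predictor validity. Under a correct model the two would generally not match, so a mismatch is not evidence against a predictor. For the same reason a match is weak evidence for one.

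The size, very roughly 20 to 70% agreement on the top predictor, depends on the assumed number, spread and type of predictors and on how concordant is defined. It is higher if one predictor dominates. It also supposes that Veterans report their drivers perfectly and that the predictors are the real drivers. With proxies, agreement would probably be lower.

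The consequence is confined to what Aim 1 may claim about its predictors from the survey. The risk score, the planned validation and the search for unmeasured barriers are untouched.

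**What to change.** Two changes to the concordant paragraph of section A4a:

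1. Replace the cohort ranking with each surveyed Veteran's own largest score contributions, for example the top three. For the logistic model these are coefficient × (own value − cohort mean). For a tree or support vector machine, use per-patient contributions. Map them to the Table 1 constructs before comparing them with the answers, and report the comparison descriptively. Mapping helps only partly where a predictor is a demographic proxy, which is why the second change is also needed.
2. Reword the validity sentence, for instance: *Validity of the predictors is judged by performance in held-out data, as already planned; the survey is used to identify candidate barriers not captured in the EHR.*

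The cost is a few lines of code on the fitted model and a small change of text, with no extra surveys or patients. The downside is a weaker claim from the survey.
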